4.4. Potential Benefits of the Proposed Research to the Subjects and Others

Subjects will benefit by receiving medication at no cost during the duration of time on study treatment (28 weeks) and daily monitoring of signs and symptoms of depression and suicide (approximately 7 months).

In case participants do suffer a relapse or side effect from change in formulations, their bupropion pharmacokinetics will be examined to determine bioequivalence. If it can be determined that clinical worsening was attributable to a non-bioequivalent switch, this information will be provided to the patient and their treating physician. The patient and their treating physician will also be informed of the bupropion XL formulation associated with clinical worsening. Such participants would benefit from learning which bupropion products are less tolerated or ineffective for them.

Society will benefit from a better understanding of the quality, bioequivalence and therapeutic equivalence of bupropion 300mg XL products.

4.4.1 Why Risks to Subjects Are Reasonable in Relation to Anticipated Benefits to Subjects

In general, the risks to research subjects in this protocol are probably small and not different than the usual manner in which generic-generic switches occur. There will be no change to the subject's prescribed medication. There is a small potential for clinical ineffectiveness, or new or worsening side effects, due to non-bioequivalence, but in such cases participants will benefit from acquiring the knowledge of which bupropion forms are non-equivalent for them. The overall anticipated benefit to society is improved bupropion 300mg XL dosing guidelines in treatment of depression. These potential benefits are substantial in comparison to the potential risks, hence the risks to subjects are reasonable in relationship to the anticipated benefits.

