2.6.5.3 Smart phone-based Assessments

Standard clinical measures of depressive symptoms are sufficient for detecting relapse, but may be insufficiently sensitive for more subtle changes caused by nonequivalent medication versions. Measuring patients' perspectives on complex, subjective, and often transient events such as symptoms or side effects is a methodological challenge, given both insight and memory biases that affect standard retrospective questionnaires.^{47,48}

Therefore, to gather more frequent and potentially more precise information, daily symptoms and side effects will be assessed via a validated smart phone-based program. This approach (Ecological Momentary Assessments, EMA) is currently in use with other Washington University in St. Louis IRB-approved protocols. Specific procedures include:

- In-person demonstration of the smart phone application with a practice phone at the start of the study.
- Phones will be provided by the study team, and run only the EMA program (i.e., no other applications or calls).
- Participants receive a daily trigger for an assessment, with reminder cues until it is completed.
- The daily assessment (approximately 20 items) will measure: (a) depressive symptoms, using 8 items from the MADRS (excluding the suicide item and the depression observational item), (b) 6 most common self-reported side effects of bupropion, as assessed in the Antidepressant Side-Effect Checklist: dry mouth, insomnia, headache, nausea, agitation and sweating, and (c) a short list (no more than 6) symptoms reported by patients who have reported problems with switching between forms of bupropion.
- Data are automatically uploaded to the University server. They will be reviewed approximately weekly.

Smart phone-based assessments are for research only, and will not be used to determine if patients have a change in clinical response to bupropion, or if subjects should be withdrawn for therapeutic reasons. This will be made clear to subjects.

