3.4.4. Suicide Risk Management

Suicide is a risk of depression and not of the study per se. Patients who are identified as having suicidal ideation will be excluded from the study. Nevertheless, since the rate of completed suicide in the USA remains high (i.e., about twice the rate of homicide) and most Americans who commit suicide suffer from depression, all subjects eligible to participate in this study are statistically at a relatively higher risk for suicide than the general population. The subjects' absolute risk for completing suicide during this brief study remains very low and participation in the study does not create or increase the risk of completed suicide. Furthermore, all participants will be formally assessed every 3 weeks during the study. If the study personnel identify that a subject has become acutely suicidal, this subject will be referred to a mental health professional for further evaluation and treatment. This may lead to a clinical intervention that is lifesaving and may not have occurred had the subject not been participating in the study.

At each assessment point, trained research staff will probe for passive death wish, and suicidal ideation, intent or plan when they administer the MADRS. If a subject endorses suicidal ideation, intent, or plan, research staff is trained to follow an operationalized protocol developed to manage high-risk subjects in other studies of depressed subjects potentially at risk for suicide. This protocol has already been used successfully by the investigators to manage several acutely suicidal patients, and entails a specific determination of the suicidal risk and a prescribed set of actions. If a subject is determined to be at high and immediate risk, research staff is instructed to stay with the subject until a study psychiatrist has been contacted to discuss the situation. Coordinators will have cell phones and at least one study psychiatrist will be reachable at all times. In case of extreme emergency, coordinators are instructed to call their hospital security team or 911 for immediate help and to initiate commitment proceedings.

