3.5 Plans for Ensuring Necessary Medical Intervention

Subjects will remain under the care of the practitioner who is their treating physician. Subjects will be instructed to inform their treating physician of participation in the research study. Subjects will be told that in the event of a physical injury as the direct result of study procedures, they will be cared for by a member of the investigating team at no cost, within the limits of the Washington University compensation plan. Drug doses are chosen to be the same as currently used for medical management of depression. Side effects for each drug will be monitored daily by trained research personnel and the PIs.

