4. HUMAN SUBJECTS RESEARCH

4.1 Protection of Human Subjects

4.1.1 Human Subjects Involvement and Characteristics

The 28-week prospective, randomized, double-blinded, crossover study will involve enrollment of 75 subjects age 18-75 vrs who volunteer and meet all inclusion/exclusion criteria. All subjects will have been diagnosed with Major Depressive Disorder (MDD) and be taking bupropion HCl, 300mg XL (branded or generic versions). After all study related procedures, risks and benefits are explained and discussed, potential subjects will be asked to sign an informed consent form approved by the Washington University Institutional Review Board (IRB) and will be enrolled. The randomization table will be generated and kept by the Barnes-Jewish Hospital Investigational Pharmacy. Subjects will complete baseline research assessments conducted by trained research staff which include a) diagnostic and symptomatic measures of depression, b) review of medical conditions and medications, c) alcohol and drug use, and d) physical health. Subjects will remain on their own medication for the initial 4 weeks of the study. During this time they will undergo daily monitoring with smart phone-based Ecological Momentary Assessments (EMA). Upon completion of this 4 week period, subjects will visit the clinic for assessment of depression and side effects. Non-adherent subjects will be withdrawn from the study. Ongoing study participation will include 6 weeks on each of the four bupropion products (brand and 3 generics) without washout between drug crossover. Subjects will participate in overnight pharmacokinetic sessions at the Washington University Clinical Research Unit (CRU) approximately 2-3 weeks following each drug crossover. These sessions will occur 4 times and involve collection of blood and urine samples for up to 24 hours. Subjects will be provided with 3 weeks of study drug prior to discharge from the CRU. Periodic (approximately every 3 weeks) interviews will be conducted at WU Medical Center research offices and include monitoring of drug compliance (MEMS 6 TrackCap system), structured interview for assessment of depression symptoms, completion of Montgomery-Asberg Depression Rating Scale (MADRS) and assessment of drug effect(s). Subjects will receive an additional 3 week supply of study drug at each clinic visit. Subjects will complete smart phone-based EMA daily for real-time capture of patientreported drug effects. Phones will also be used as a reminder to adhere to dosing instructions and provide instructions and trouble-shooting guidance. At the conclusion of the final session and last clinic visit, subjects will be returned to their original bupropion formulation and directed to resume their own medication. All studies are conducted under the supervision of the PI, a Board-Certified and GCP-certified and clinically active anesthesiologist with extensive experience in the conduct of human volunteer studies. We will examine bioequivalence, clinical equivalence, stereoselectivity, genomics, and patient perspectives regarding switches between commercially available forms of bupropion 300mg XL.

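### Section 4.4 promises daily suicide monitoring that no procedure provides, and 3.5 promises daily staff monitoring of side effects where scheduled staff review is about weekly or at visits

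*Combined protocol and SAP*

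**What the plan says.** Two sections describe daily monitoring.

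- Section 4.4 gives every subject two benefits: free medication and "daily monitoring of signs and symptoms of depression and suicide (approximately 7 months".
- Section 3.5 states: "Side effects for each drug will be monitored daily by trained research personnel and the PIs".

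Four places describe what is actually done.

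- Section 2.6.5.3 defines the daily phone assessment. Its depression part is built by "using 8 items from the MADRS (excluding the suicide item and the depression observational item". It also covers six side effects and a short list of switch-related symptoms. On staff review of the data it says: "They will be reviewed approximately weekly". On their use it says: "Smart phone-based assessments are for research only". The study phones "run only the EMA program (i.e., no other applications or calls".
- Section 3.4.4 says that, at each assessment point, "trained research staff will probe for passive death wish, and suicidal ideation, intent or plan when they administer the MADRS", and it puts formal assessments three weeks apart.
- Section 4.1.1 gives the same rhythm: "Periodic (approximately every 3 weeks) interviews will be conducted at WU Medical Center research offices".
- The Study Table marks both the MADRS and the ASEC at ten visits: Visits 0 to 5 and PK sessions 1 to 4.

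**The concern.** Section 4.4 credits the design with something it does not have. The phone assessment is the only symptom measure taken every day, and 4.1.1 also calls it daily monitoring, so it is the natural referent of the phrase in 4.4. Yet it deliberately asks nothing about suicide. Section 3.5 differs in kind: side effects are recorded daily, but by the subject, while the sentence names staff and the PIs as the people who monitor.

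This matters because the population has MDD and is switched blind between products. Section 3.3.2 calls the risk of an ineffective or poorly tolerated product unknown, and section 3 allows for relapse with suicidal ideation. Ethics reviewers read 4.4 and 3.5 as statements about safety. Section 4.3.2 says subjects get written descriptions of procedures, risks and benefits, so the same statement could reach them. Staff following 2.6.5.3 would also not be doing what 3.5 says they do.

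**Working it through.** No power or sample-size figure is involved. The check is a count of contacts, followed by a comparison of the sections.

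**Inputs.** Lead-in of 4 weeks and four 6-week periods (2.6.1); PK visit in the day 10–20 window and a second visit in week 6 of each period (2.6.5); MADRS row of the Study Table; review frequency of phone data (2.6.5.3). I take Visit 0 as day 0.

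**Study length.** 4 + 4 × 6 = 28 weeks, which reproduces the plan's figure. 28 × 7 = 196 days, or 196/28 = 7 four-week months, in line with the duration in 4.4.

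**Scheduled suicide probes.** Visit 0 + Visit 1 + 4 periods × 2 visits = 10, matching the ten marks in the table. Visit 0 is the consent and eligibility visit, so 10 − 1 = 9 probes follow it.

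**Spacing.**
- Whole study: 196/9 = 21.8 days on average.
- Crossover: (4 × 42)/8 = 168/8 = 21.0 days on average.
- Lead-in: 28 days, on the subject's own product.
- PK visit to week-6 visit: from 36 − 20 = 16 days to 42 − 10 = 32 days.

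**Phone data.** About 196 daily entries, of which 0 contain a suicide question. Weekly review gives 196/7 = 28 staff reviews.

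**Statement against procedure.**

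| Stated as daily | What the procedures provide |
|---|---|
| Depression monitoring (4.4) | Eight MADRS items self-reported daily; staff review about weekly, research only; full MADRS at visits |
| Suicide monitoring (4.4) | Nothing daily; staff probe with the MADRS at Visit 0 and 9 later visits |
| Side-effect monitoring by staff and PIs (3.5) | Six side effects self-reported daily; staff review about weekly; weekly team meeting (3.4); ASEC at visits |

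The first row is met as data collection but not as daily staff review. The second is not met in any form. The third is met as self-report, but not by the people the sentence names.

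The other safety provisions do not fill the gap. The 24-hour answering service (3.4) and pager access (Study Table) depend on the subject making contact. The ad hoc phone calls in the Study Table have no schedule. None is daily monitoring.

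**The case against.** The strongest reply is that the operative text is clear and consistent. Sections 2.6.5.2, 3.4.4 and 4.1.1 all give the three-week rhythm, 3.4.4 adds an escalation procedure, and staff work from those sections rather than from a benefits sentence. That stands, and it is why the point is minor. It does not make the sentence in 4.4 true.

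On 3.5, one can read daily monitoring as daily capture by phone. The sentence does not mention phones or data review, so it is loose rather than a clear rival review schedule. But it names staff and the PIs as the monitors, and no scheduled daily staff activity exists, so clarification is still warranted. For the same reason, a ratio of daily to weekly reviews would measure nothing: it restates the two words and assumes that 3.5 refers to reading phone data.

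Some stronger readings are tempting, and the documents do not support them.

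- *Suicide surveillance is inadequate, and the gaps of up to 32 days show it.* The gaps follow from a visit schedule chosen on purpose, with a 24-hour service alongside. They describe the schedule; they do not measure an error.
- *All of 4.4's daily monitoring is missing.* The depression half is met as daily self-report.
- *Subjects are misled, and may fail to call for help.* The consent form is not in the documents. Section 2.6.5.3 promises to make the research-only status clear, and the Study Table provides orientation at Visit 0 and reinstruction at later visits. Harm through consent is a possibility, not a finding. What 2.6.5.3 does not promise is to tell subjects that suicide is not asked about or that entries are not read daily.
- *Phone data should therefore trigger contact.* That would conflict with their research-only status. It could also lead to extra MADRS assessments. Under 2.7.3.3 a MADRS rise of 2 points, or a score of 15 or more, leads to a SCID, and confirmed MDD means relapse and removal. Ascertainment of the main clinical outcome could change.

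**Conclusion.** The inconsistency is real and minor. Daily suicide monitoring in 4.4 has no procedure behind it: no phone entry asks about suicide, and the scheduled probes are the eligibility screen plus 9 visits averaging 21.8 days apart. Section 3.5 attributes daily side-effect monitoring to staff and the PIs, although the daily element is self-report and scheduled staff review is about weekly or at visits.

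The spacing assumes the nominal calendar and Visit 0 on day 0; the conclusion does not depend on either. It rests on the procedures the protocol describes and makes no claim about the consent wording. Endpoints, visit schedule, sample size and analysis are unaffected.

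**What to change.** - **4.4:** replace the monitoring phrase with a statement that subjects self-report depressive symptoms daily by phone, for research only, and that trained staff assess depression and suicidal ideation at scheduled visits about every three weeks, 9 of them after the eligibility visit.
- **3.5:** state that subjects self-report six side effects daily, that staff review these about weekly for research, and that the ASEC at visits is the clinical assessment.
- **Visit 0 training:** tell subjects that the phone does not ask about suicide and is not read daily, and that urgent concerns go to the 24-hour service.
- **Consent form:** align it if it repeats 4.4.

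Phone data should stay research-only, with no contact trigger added. The cost is wording in two sections and a short statement in a training session that already takes place. There are no added visits or assessments and no change to outcomes or analysis.

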4.5 Subject Compensation

Subjects are compensated for participation. A subject will receive \$150 for completing the 4 week lead-in, and \$250 for completing each of four 6-week drug evaluation periods (up to \$1150). If they complete the entire protocol they will receive an additional \$850. Maximum total compensation is therefore \$2000. If a subject stops participating before the entire protocol is completed, they will receive the prorated amount for the number of sessions completed.

4.6 Importance of the Knowledge to be Gained

More than 3 billion generic drug prescriptions are filled annually in the US, and generic medicines save consumers and the U.S. healthcare system \$190 billion annually. Generic drugs are usually only approved after demonstration of bioequivalence to the innovator (branded) drug. Bupropion is taken by more than 1 million Americans annually. One generic formulation of bupropion was recently found to be non-bioequivalent and withdrawn from the market. It is important that the bioequivalence of other bupropion 300mg XL products be assessed and verified.

4.7 Inclusion of Women

There is no exclusion of any sex/gender or racial/ethnic group for these studies. Studies and their advertisements actively encourage the participation of women in the research. The study goal is equivalent numbers of women and men. To ensure sufficient enrollment of both sexes, enrollment is typically closed once a sex quota is reached. Women of childbearing excluded. Bupropion is not contraindicated during potential are not pregnancy (http://www.womensmentalhealth.org/use-of-wellbutrin-bupropion-during-pregnancy/). Subjects will be advised to follow the instructions of their bupropion-prescribing physician regarding pregnancy or pregnancy planning, and, per drug label, to inform the investigators and their treating physician if they become pregnant or intend to become pregnant during the course of the study.

4.8 Inclusion of Minorities

Studies and their advertisements actively encourage the participation of minorities in the research. Minority recruiting typically matches the demographic composition of the Washington University community from which subjects will be recruited (44% white, 51% Black, 2% Asian, 2% Hispanic).

4.9 Inclusion of Children

Subjects <18 yr will not be studied in these investigations.

4.10 Clincaltrials.gov requirements

The proposed research will be registered in ClinicalTrials.gov once the protocol has been reviewed and approved by the FDA RIHSC.

- 51. Bioequivalence evaluation of innovator and generic bupropion XL products: Final report. US Food and Drug Administration, Center for Drug Evaluation and Research, Division of product quality research 2012: http://www.fda.gov/downloads/Drugs/DrugSafety/PostmarketDrugSafetyInformationforPatientsandProviders/UCM32 3471.pdf

Bioequivalence and clinical effects of generic and brand bupropion: Study Table

		Pre- Randomization Study Period (24 weeks)										Entire	Post
		randomization (4 weeks) Initial clinic Lead-in	otaay Drag .		Study Drug 2		Study Drug 3		Study Drug 4			Study	Study
Procedure			Random ization		Study clinic	PK Session	Study clinic	PK Session	(6 we Study clinic	PK Session	Close-out Clinic		
		Visit 0	Visit 1	1	Visit 2	2	Visit 3	3	Visit 4	4	Visit 5		
Subject visit		1	2	3	4	5	6	7	8	9	10		
Subject contacts investigators. Telephone description of study purpose, procedures, benefits, risks. Screen potential eligibility. (E)mail informed consent doc to subject. Subject contacts investigators if interested	X												
Review study purpose, procedures, benefits, risks. Provide detailed orientation to study procedures (daily smart phone assessments, medications)		X											
Informed consent		X											
Structured Clinical Interview for DSM-IV Axis I Disorder (SCID) (as needed)		Χ	(X)	(X)	(X)	(X)	(X)	(X)	(X)	(X)	(X)		
MADRS -Symptoms of depression questionnaire		Χ	Χ	Х	Χ	Х	Χ	Х	Χ	X	Х		
ASEC checklist (side effects)		Χ	X	Х	Χ	Х	Χ	Х	Χ	Х	Х		
Training: Daily smart phone assessments and MEMS 6 TrackCap use		Χ											
Determine and confirm eligibility		Х											
Replace subject's current bupropion product with same product, over- encapsulated (4 wk supply)		Х											
Randomization			X										
Subject starts new crossover bupropion study drug			X		X		X		X				
Provide over-encapsulated study drug(3 wk supply)			X	X	Χ	X	Χ	X	X	X			
Download MEMS compliance data			X	X	Χ	X	Χ	X	X	X			
Review smart phone, download data (if required)			Χ	Х	Χ	Х	Χ	Х	Χ	X	Х		
DNA sample (blood)				Х									
24 hour PK session, venous sampling (~15 samples, 75ml)				Х		Х		Х		X			
24 hour urine collection				Х		Х		Х		X			
Reinstruct subjects to all study related procedures			Χ	Х	Χ	Х	Χ	Х	Χ	X	Х		
Subject performs daily smart phone-based assessments												Χ	
Capture drug compliance and adherence (MEMS 6 TrackCap)												Χ	
Occasional phone calls if warranted												Χ	
24 access via pager to Research Team and Research MD												Χ	
Return subjects' original bupropion medication											X		 
Remuneration for study participation (and completion)			X		Х		X		X		Х		
Collect all study equipment (phone, MEMS 6 TrackCap)											Х		
30 day telephone follow-up													X
